#### 5.6.2 Adverse Events

The analysis of AEs will use the SFAS.

The investigator determines the intensity of AEs and the relationship of AEs to study medication. In tabular summaries, TEAEs will be sorted by descending percentage in all participants. TEAEs will be summarised overall, by induction arm, and within individual randomisation strata.

The number and percentage of participants reporting TEAEs will be tabulated overall by SOC and PT, by PT, and by severity, SOC, and PT. If more than 1 TEAE is coded to the same PT for the same participant, the participant will be counted only once for that PT using the most severe occurrence for the summarisation by severity.

In addition, the following categories of TEAEs will be tabulated:

- Severe, by SOC and PT
- Serious, by SOC and PT
- Serious AE meeting the criterion "Laboratory values of ALT or AST >3×ULN and bilirubin >2×ULN", by PT
- Fatal, by PT
- Adverse events of special interest, by PT
- Drug-related Hepatic Disorders and Injection Reaction Events, per the customised MedDRA Query (CMQ) definitions (see Section 6.7), by SOC and PT
- Related to TM BUP, by SOC and PT
- Related to RBP-6000, by SOC and PT
- Leading to treatment discontinuation from TM BUP (action taken is "Drug withdrawn" per eCRF), by SOC and PT
- Leading to treatment discontinuation from RBP-6000 (action taken is "Drug withdrawn" per eCRF), by SOC and PT
- Reported as opioid withdrawal symptom, by SOC and PT
- •

The number and percent of participants with at least 1 event in the above categories will be presented on an AE summary table.

For the SoC arm, the number and percentage of participants reporting TEAEs during the Run-in Period (TEAEs with a start date on or after the first dose of TM BUP and before the datetime of Injection 1) will be tabulated overall by SOC and PT.

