In INDV-6000-403 (which used the more rapid induction that is also explored in this current protocol), the most commonly reported treatment-emergent AEs (TEAE) were irritability, anxiety, nausea and pain. The majority of participants reported TEAEs within 48 hours of RBP-6000 administration. Overall, the AE profile and level of sedation indicate that it is safe and tolerable to initiate RBP-6000 following a single dose of TM buprenorphine. There were no unexpected safety findings.

Like the participants in Study INDV-6000-403, participants in the current study will be treatment-seeking but still using opioids, which puts them at high risk for rapid and intense onset of withdrawal symptoms if buprenorphine is administered too soon after their last use of a full opioid agonist. The risk is increased with high doses of potent opioids, such as fentanyl, thus, an on-site dipstick UDS at Screening to identify current

opioids of abuse will support this discussion between the Investigator and study participant. As supported by the results of Study INDV-6000-403, this risk is also mitigated by the requirement for participants to be in withdrawal prior to receiving the first dose of TM buprenorphine. A single dose of 4 mg TM buprenorphine should be sufficient to identify hypersensitivity to buprenorphine and to minimise the occurrence of precipitated withdrawal (as a result of the participant inadequately/incorrectly reporting use of long- or short-acting opioids). Also, use of concomitant medications is permitted to alleviate any withdrawal symptoms that occur, such as ondansetron for nausea/vomiting, clonidine for anxiety/irritability and ibuprofen for pain/body aches, in accordance with SAMHSA TIP 63 2020 guidelines. In addition, following the first injection of 300 mg RBP-6000, TM buprenorphine in increments of 2 to 4 mg up to a maximum dose of 12 mg (inclusive of pre–RBP-6000 TM buprenorphine) may be administered on Day 1 at the discretion of the Investigator to alleviate withdrawal symptoms while on site.

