14.10 Safety Analysis

Safety data will be analysed using descriptive statistics for continuous endpoints and frequency counts with percentages for categorical endpoints. For RBP-6000 Open-label and Double-blind Safety Populations, safety data will be assessed by treatment group and overall for the OLTP and for the DBTP. The TM Buprenorphine Safety Population will also be used for summarising safety measures for the induction period. Complete details of the safety analyses will be provided in the SAP.

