**Table 5. Populations for Analysis** 

Population	Description
Screened	All participants who sign the informed consent form.
Sub-study Randomised Population (SRP)	The SRP will comprise all participants who give informed consent and are randomised to sub-study treatment. The participants will be analysed corresponding to the induction arm to which they were randomised (ie, planned arm).
Sub-study Full Analysis Set (SFAS)	The SFAS will comprise all participants who are randomised to sub-study treatment and receive the first dose of TM BUP and do not demonstrate idiosyncratic response to the first dose of TM BUP (ie, allergic / hypersensitivity reaction to TM BUP as recorded on the electronic case report form [eCRF] disposition). The participants will be analysed corresponding to the induction arm they received ("as treated", ie, actual arm), given that logistically it is highly unlikely for them to receive the induction arm that they were not randomised to since the randomised arm triggers eCRF forms corresponding to the schedule of events for that arm. Participants who were randomised and inducted with neither RI or SoC (which is a key protocol deviation) will be excluded from the SFAS. The SFAS will serve as the primary population for the analysis in this sub-study.
Evaluable Population for Treatment Retention/Discontinuation a	For analysis pertaining to treatment retention and time-to-treatment discontinuation, the SFAS participants who discontinue treatment within the sub-study due to not meeting Inclusion/Exclusion criteria will be also excluded. The participants will be analysed corresponding to the induction arm they received ("as treated", ie, actual arm).

a Note that this population is described in the protocol but was not given a distinct population name. It is named in this statistical analysis plan for ease of reference and clarity in estimand and analysis specifications.

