#### 5.4.1.3 Exploratory analysis approach

The completion rate for the OLIS (ie, receiving double-blind RBP-6000 Injection 3) will be estimated by Bayesian beta-binomial model using non-informative uniform prior, ie, Beta (1,1), within individual induction arms. The posterior distribution of completion rate difference between the 2 arms will be obtained and presented in a similar way as the primary endpoint, treatment retention rate at injection 2.

## 5.4.2 Secondary endpoints 2 and 3: The proportion of participants reporting adverse events up to Injection 2, and between Injections 2 and 3

The analysis of secondary endpoints 2 and 3 will use the SFAS.

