### 5.4.2.2 Main analytical approach

The number and proportion of participants with at least 1 TEAE, treatment-related TEAE, serious TEAE, fatal TEAE, serious TEAE meeting LFT criteria, severe TEAE, TEAE leading to discontinuation, or TEAE reported as adverse events of special interest, drug-related hepatic disorders (see definition in Section 6.7.1), injection site reactions (see definition in Section 6.7.2), opioid withdrawal symptoms, and precipitated withdrawal symptoms (per eCRF) will be summarised for each endpoint, by induction arm within randomisation strata and for overall.

The numerator of the proportion for each endpoint will be the number of participants with at least 1 TEAE of interest in the respective time interval. The denominator for endpoint 2 (TEAEs up to RBP-6000 Injection 2) will be the number of participants in the SFAS population. The denominator for endpoint 3 (TEAEs between RBP-6000 Injections 2 and 3) will be the number of the participants in the SFAS population who received Injection 2.

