## 5.6 Safety Analyses

## 5.6.1 Extent of Exposure

The extent of exposure analyses will be performed for the SFAS using descriptive statistics.

For both treatment arms, the following summaries will be performed:

• Total number of RBP-6000 injections received in the OLIS (ie, 0-3)

- - Number of participants who received RBP-6000 at each injection (Injections 1 through 3)
  - Total number of induction attempts
  - Total dose of TM BUP on the most recent induction day
  - Total dose of additional (post-injection) TM BUP during the first 5 hours of the most recent induction day

For the RI arm, the following summaries will be performed:

- the total dose of pre-injection TM BUP on the most recent induction day.
- the time elapsed between TM BUP and Injection 1 on the most recent induction day, overall

For the SoC arm, the following summaries will be performed for the participants who received RBP-6000 injection:

- The number of days of dose stabilisation (ie, number of days of SoC Induction with TM BUP prior to the first injection of RBP-6000). The number of days will be calculated as the date of the first dose of TM BUP minus the date of the last dose of TM BUP plus 1. A categorical data summary using categories <7, 7, 8, and >8 will be performed, as well as a continuous data summary.
- The average daily TM BUP dose during the SoC induction phase, calculated as the total cumulative dose divided by the number of days of dose stabilisation.
- The total TM BUP dose on the day prior to first injection of RBP-6000 (Day -1, as collected on the eCRF).

Participants who take TM BUP after Week 1 Day 1 will be presented in a data listing. Use of TM BUP after Week 1 Day 1 is prohibited per the protocol, but if it occurs, the information would be captured on the concomitant medication form of the eCRF.

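### The sub-study's AE and exposure tables use a set that excludes recorded first-dose hypersensitivity reactions, so those events count as zero by definition

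*SAP*

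**What the plan says.** SAP Table 5 admits to the SFAS randomised participants who receive the first TM BUP dose and who "do not demonstrate idiosyncratic response to the first dose of TM BUP (ie, allergic / hypersensitivity reaction to TM BUP", as recorded on the eCRF disposition. It also removes participants inducted with neither rapid induction (RI) nor standard-of-care induction (SoC). The other sets in Table 5 are the Screened population, the Sub-study Randomised Population (SRP) and the Evaluable Population for retention. None of them is a safety population.

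The SFAS is then used for safety throughout:

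- AE tables (SAP 5.6.2): "The analysis of AEs will use the SFAS".
- Safety endpoints (SAP 5.4.2): "The analysis of secondary endpoints 2 and 3 will use the SFAS". For Endpoint 2, SAP 5.4.2.2 adds: "The denominator for endpoint 2 (TEAEs up to RBP-6000 Injection 2) will be the number of participants in the SFAS population".
- Exposure (SAP 5.6.1): "The extent of exposure analyses will be performed for the SFAS using descriptive statistics".
- Concomitant medications (SAP 5.7.1), and vital signs, weight, ECG and liver tests (SAP 5.6.3 to 5.6.6), also use the SFAS.

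**The concern.** Membership of the set used for safety depends on not having had a particular adverse drug reaction. Excluding these participants can be defended for retention, where the question is whether a participant who tolerates the drug goes on to Injection 2. For AE incidence, the same rule removes the event and the person together.

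The reaction matters to the design. Protocol 1.3.1 says of the test dose: "A single dose of 4 mg TM buprenorphine should be sufficient to identify hypersensitivity to buprenorphine". The sub-study AE tables cannot count the event that this dose is meant to reveal. SAP 5.1.1 and 5.8 also allow the sub-study results, secondary endpoints included, to go into an interim study report for regulators. A reader of such a report would see a zero that was fixed by definition and could take it as an observation.

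**Working it through.** **1. Follow one participant through the rules.** Someone is randomised, takes the first TM BUP dose and has an allergic reaction.

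- SAP 5.4.2.1 opens the treatment-emergent window at the first TM BUP dose, so the reaction is a TEAE in the interval up to Injection 2.
- Protocol 4.1.2 requires discontinuation from the study. The event therefore belongs in the SAP 5.6.2 table of TEAEs leading to discontinuation of TM BUP and, if judged related, in the TM BUP-related table. If it were serious or fatal, it would belong in those tables too.
- SAP Table 5 removes the participant from the SFAS once the reaction is recorded on disposition. The participant then leaves both numerator and denominator of all these tables.

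**2. Compare with the protocol.** Protocol Appendix 22.9, section 3, states the idiosyncratic-response exclusion for retention and for time to discontinuation. The AE endpoint in the same list carries no such exclusion. Section 8.8.2 of that appendix plans to list and summarise events from the first induction dose up to Injection 3, again without it. Section 8.8 leaves full safety details to the SAP. However, section 8.4.2 makes the SFAS the primary sub-study population, and section 8.9 names it for concomitant medications.

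**3. Which summaries the hypersensitivity exclusion changes.** These participants are stopped before any RBP-6000.

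- Changed: Endpoint 2, overall and TM BUP-related AE tables, exposure, and concomitant medications up to Injection 2.
- Essentially unchanged: Endpoint 3 (its denominator requires Injection 2), the RBP-6000-related tables, and later vital signs, ECG and liver tests. After TM BUP only, early termination is a phone contact limited to ongoing AEs and associated medications (Protocol 6.4 and Appendix 22.6).

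**4. Illustrate the size.** No plan figure is in dispute. For a denominator, take the planned 489. This is consistent with Appendix 22.9, section 5: 390/(1 − 0.20) = 487.5, rounded up to 488, one below the stated 489. Assume for illustration that all 489 are dosed, that *k* have a recorded first-dose reaction, and that nobody is excluded for another reason. The values of *k* are assumptions chosen to show the mechanism.

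- On the SFAS: 0/(489 − *k*). The exact one-sided 95% upper bound for zero events is 1 − 0.05^(1/(489 − *k*)).
- On all dosed: *k*/489. The exact bound is the *p* for which P(X ≤ *k*) = 0.05 with X ~ Binomial(489, *p*).

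| *k* (assumed) | SFAS | Upper bound | All dosed | Upper bound |
|---|---|---|---|---|
| 1 | 0/488 | 0.61% | 1/489 = 0.20% | 0.97% |
| 3 | 0/486 | 0.61% | 3/489 = 0.61% | 1.58% |
| 5 | 0/484 | 0.62% | 5/489 = 1.02% | 2.14% |
| 10 | 0/479 | 0.62% | 10/489 = 2.04% | 3.44% |

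The SFAS columns hardly move with *k*, so the table carries no information about this reaction. The SAP plans only counts and percentages for AEs. The bounds show what a reader might reasonably attach to a zero.

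**5. The second exclusion.** Participants inducted with neither regimen have also been dosed, and some may go on to RBP-6000. SAP 5.7.6 plans a retention analysis for them but no AE summary. Their AEs, including any after RBP-6000, drop out of the sub-study tables. The protocol's SFAS definition does not contain this second exclusion.

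**The case against.** The strongest reply has five parts.

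- **The secondary objective concerns RBP-6000.** Participants who react to the first TM BUP dose never receive it. This stands: a reader might infer that RBP-6000 injection safety is biased by the hypersensitivity exclusion, and the documents do not support that. But the SAP chose to tabulate TM BUP-related events and to start the clock at the TM BUP dose, so those tables should be able to count them.
- **The cases are reported elsewhere.** A reader might infer that they vanish altogether; they do not. SRP disposition gives discontinuations with reasons (SAP 5.2.2), and listings cover the Screened population (SAP 5.1.2). For the main study, Protocol 14.10 says: "The TM Buprenorphine Safety Population will also be used for summarising safety measures for the induction period". That set's definition is not in the visible text, so whether it keeps these cases cannot be settled. Disposition and listings do not give incidence by preferred term, severity or relatedness. The main-study open-label safety population requires an RBP-6000 injection and so cannot include first-dose reactors.
- **Numbers will be small.** Probably so: exclusion criterion 11 removes known hypersensitivity. The documents give no rate, so no expected count can be claimed. It would also go too far to assume that these events are serious. The protocol requires discontinuation, and seriousness depends on the general definition in Protocol 11.1.
- **The zero is conditional.** This stands. Reactions to later doses stay in, as would a first-dose reaction entered only as an AE and not on disposition. Both arms face the same rule, and no between-arm distortion is shown.
- **The SAP follows the protocol's SFAS definition.** This is true for the hypersensitivity exclusion. It explains where the rule came from, but it does not make the set suitable for AE incidence.

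**Conclusion.** The point holds for the sub-study's Endpoint 2, AE, exposure and concomitant-medication summaries. A first-dose allergic or hypersensitivity reaction recorded on disposition is a TEAE under the SAP but has a count of zero by definition in the sub-study AE tables. For this event the error can only lower the reported count.

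The size is unknown and probably small. It concerns TM BUP and induction-phase safety. The omission of dosed participants inducted with neither regimen is a separate loss that can extend to events after RBP-6000. The conclusion rests on the population definitions alone and does not depend on any assumed reaction rate. It should be fixed, but it does not threaten the retention result or the main study's dose comparison.

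**What to change.** Add to SAP Table 5 a Sub-study Safety Population: all randomised participants who received at least one dose of TM BUP, analysed by induction received, with any participant inducted by neither regimen shown in the Total column.

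- Use it for SAP 5.4.2, 5.6.1 and 5.6.2 and for the concomitant-medication summaries. Endpoint 3 keeps its restriction to those who received Injection 2.
- Sections 5.6.3 to 5.6.6 may follow for consistency, although little will change there.
- Keep the SFAS and Evaluable Population for retention and time to discontinuation.
- Record the change in SAP Appendix 6.2, because Protocol Appendix 22.9, sections 8.4.2 and 8.9, names the SFAS.

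The cost is one population flag and revised SAP wording. No new data are needed. Reported AE rates may rise slightly.

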#### 5.6.3 Vital Signs

The vital signs (systolic blood pressure, diastolic blood pressure, pulse rate, respiratory rate), at each nominal scheduled visit, using the most recent induction attempt, will be summarised overall, by induction arm, and within individual randomisation strata at each visit for the SFAS.

Data collection of body temperature was allowed by methods axial, forehead, oral, or ear. Since temperatures may vary somewhat by method, the temperature data will only be listed.

#### 5.6.4 Body Weight and BMI

The results of scheduled assessments of body weight and BMI will be summarised overall, by induction arm, and within individual randomisation strata at each nominal visit for the SFAS.

#### 5.6.5 Electrocardiograms

At each nominal scheduled visit using the most recent induction attempt, electrocardiogram (ECG) numeric variables (heart rate, PR interval, QRS duration, QT Interval, and QT interval corrected using Fridericia's method, QTcF, change from screening for QTcF) will be summarised overall, by induction arm, and within individual randomisation strata for the SFAS. In addition, the number and percentage of participants with QTcF >500 msec and with the QTcF change from Screening to each nominal scheduled visit >60 msec will be summarized overall, by induction arm, and within individual randomisation strata for the SFAS.

The investigator's assessment of ECG results (normal/abnormal and if abnormal, clinically significant yes/no) will be listed.

#### 5.6.6 Liver Function Tests

The following liver functions tests (LFTs) will be collected according to the protocol schedule of events: alkaline phosphatase, alanine aminotransferase (ALT), aspartate aminotransferase (AST), total bilirubin, albumin, total protein, gamma glutamyl transferase, and lactase dehydrogenase. Analysis of LFTs will use the SFAS.

### 5.6.6.1 Factors of Upper Limit of Normal

The number and percentage of participants meeting liver function test criteria for ALT, AST, and total bilirubin during the timeframe after the first dose of TM BUP up to and including Week 6 will be summarised overall, by induction arm, and within individual randomisation strata. For each lab parameter, the participant will be counted only once according to their worst case (highest) result during the timeframe. The criteria are factors of upper limit of normal (ULN), as follows:

- a. ALT (>3×ULN)
  - >=8×ULN
  - >=5×ULN to <8×ULN

  - >3×ULN to <5×ULN

- b. AST (>3×ULN)
  - >=8×ULN
  - >=5×ULN to <8×ULN

  - >3×ULN to <5×ULN

- c. Total Bilirubin (>2×ULN)
  - >=5×ULN

#### >2×ULN to <5×ULN

The LFT data will be listed for participants with values meeting these criteria.

#### 5.6.6.2 LFT values

At each nominal scheduled visit using the most recent induction attempt, LFT results and the change in LFT result from screening will be summarised overall, by induction arm, and within individual randomisation strata.

#### 5.7 Other Analyses

#### 5.7.1 Concomitant Medications, Other

The number and percentage of participants taking any concomitant medication during the time period from the first dose of TM BUP up to Injection 2 will be summarised by pharmacological group (ATC level 3) and preferred drug name for the SFAS overall and by induction arm overall and within individual randomisation strata using descriptive statistics. These analyses will include concomitant medications from all induction attempts that have a start date/time before the date/time of Injection 2.

The number and percentage of participants taking any prior medications and concomitant medications (Section 6.5) will be summarised by pharmacological group (ATC level 3) and preferred drug name for the SFAS overall and by induction arm overall and within individual randomisation strata using descriptive statistics.

#### **5.7.2** Induction Attempts

The number and percentage of participants who have multiple induction attempts will be summarised using the SFAS and descriptive statistics. The numerator will be the number of participants with >1 Induction Day 1 Visit, and the denominator will be the number of participants in the SFAS.

The number and percentage of participants who did not continue with an induction attempt, and the reasons for not continuing (as collected in the eCRF) will be summarised using the SRP and descriptive statistics. The numerator will be the number of participants with at least

1 induction attempt that was not continued and the reason for not continuing, respectively, and the denominator will be the number of participants in the SFAS and the number of attempts not continued, respectively. The summaries will be repeated for those participants who were randomised but discontinued before receiving Injection 1.

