#### 1.3 Study Design

This SAP describes the analysis for the OLIS nested within the main study, which is a randomised, double-blind, parallel group, multicentre study to compare the efficacy, safety, and tolerability of 100mg and 300-mg maintenance doses of RBP-6000 administered every 4 weeks to high-risk, treatment-seeking adult participants with moderate to severe OUD (as assessed by Diagnostic and Statistical Manual of Mental Disorders, 5th Edition [DSM-5]) who use opioids via an injection route and/or use high doses of opioids. The OLIS is designed to compare the treatment retention of all participants inducted onto RBP-6000 using SoC (minimum 7 days of TM BUP per label) with RI onto RBP-6000 treatment.

The OLIS randomisation is implemented using an Interactive Web Response System (IWRS). Participants who meet all of the eligibility criteria and all of the TM BUP dosing criteria are randomised following the first induction day urine drug screen (UDS), at a 2:1 ratio to receive either RI or SoC induction. The induction randomisation number, assigned via the IWRS, used central, blocked, stratified randomisation schedules. The stratification factor is first induction day UDS positive for fentanyl (yes or no). Participants who are randomised but do not receive TM BUP will not be replaced.

The OLIS randomisation schedules were generated using SAS v9.4 using a balanced-across-centres (BAC) approach [Song, 2003]. For the BAC approach, all permuted blocks with specified block size (size=3 with treatment ratio 2:1) were determined. Then the block order was randomly permuted to form a Latin Square, and blocks dynamically allocated to centre at the time of randomisation of the first participant. This approach helps balance the treatment assignments across centres when blocks are left incomplete.

Approximately 489 participants will be enrolled and receive RBP-6000 treatment in the OLIS in order to meet the sample size requirements for the main study.

Two interim analyses (IA) will be performed to allow early declaration of non-inferiority (NI) of RI to SoC induction with respect to treatment retention at Injection 2 (see Section 3 and Section 5.8 for details). If NI is declared at the first IA, then the second IA might not be performed.

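### SAP 5.7.2 takes the non-continued-attempt summary in the SRP but divides by the SFAS count, so the percentage exceeds the SRP proportion whenever the two sets differ

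*SAP*

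**What the plan says.** SAP 5.7.2 (Induction Attempts) contains two summaries and a repeat.

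- The first counts participants with more than one Induction Day 1 Visit. It names the SFAS as its population and divides by the SFAS count, so the two agree.
- The second counts participants who did not continue an induction attempt, with the reasons. It "will be summarised using the SRP and descriptive statistics". Its numerator sentence opens "The numerator will be the number of participants with at least" and goes on to one non-continued attempt; nothing limits those participants to the SFAS. For the denominators, "the denominator will be the number of participants in the SFAS and the number of attempts not continued, respectively".
- Both are then repeated for randomised participants who discontinued before Injection 1. No denominator is given for the repeat.

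SAP Table 5 defines the two populations differently:

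- "The SRP will comprise all participants who give informed consent and are randomised to sub-study treatment", analysed by planned arm.
- The SFAS is limited to those "randomised to sub-study treatment and receive the first dose of TM BUP and do not demonstrate idiosyncratic response to the first dose of TM BUP", analysed by the arm actually received. In addition, "Participants who were randomised and inducted with neither RI or SoC (which is a key protocol deviation) will be excluded from the SFAS".

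**The concern.** Every SFAS member is in the SRP, but the converse need not hold. A participant who is randomised and never receives TM buprenorphine, who has an idiosyncratic response, or who is inducted by neither regimen can be counted in the numerator and cannot be counted in the denominator. The resulting figure is a proportion of neither population.

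The plan itself allows for the sets to differ. SAP 1.3 says "Participants who are randomised but do not receive TM BUP will not be replaced", and SAP 5.2.2 tabulates participants who discontinue before TM buprenorphine.

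A second mismatch appears when the table is split by arm, which SAP 5.1.3 calls for where applicable. The numerator then follows planned arm and the denominator actual arm.

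What is at stake is one reported percentage and its by-arm comparison. Stopped attempts bear on how well each induction route is tolerated, so the figure should mean what its label says. No test or decision rule uses it.

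**Working it through.** The documents state no count or percentage for this summary, so there is no figure of the plan's to reproduce.

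**Notation**

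- N = number in the SRP; M = number in the SFAS, with M ≤ N by Table 5.
- X = SRP participants with at least one non-continued attempt.
- Xs = those of the X who are in the SFAS, with Xs ≤ X.

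**Three possible percentages**

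- As written: X/M
- SRP throughout: X/N
- SFAS throughout: Xs/M

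(X/M) ÷ (X/N) = N/M ≥ 1. The written rule therefore exceeds the SRP proportion whenever M < N and X > 0, whether or not the participants outside the SFAS had a stopped attempt. Against the SFAS version, X/M is higher only if at least one of them did (X > Xs).

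**Size**

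N = 489 is the planned number randomised (SAP Section 3). The share outside the SFAS is assumed.

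| Assumed share outside | Outside | M | N/M |
|---|---|---|---|
| 0% | 0 | 489 | 1.000 |
| 1% | 5 | 484 | 489/484 = 1.010 |
| 2% | 10 | 479 | 489/479 = 1.021 |
| 5% | 24 | 465 | 489/465 = 1.052 |
| 10% | 49 | 440 | 489/440 = 1.111 |

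**Worked case**

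Assume 5% outside (M = 465) and 46 SFAS participants with a stopped attempt. The number of the 24 outside who also had one is varied.

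| Of the 24 outside | X | As written | SRP throughout | SFAS throughout |
|---|---|---|---|---|
| 0 | 46 | 46/465 = 9.89% | 46/489 = 9.41% | 46/465 = 9.89% |
| 12 | 58 | 58/465 = 12.47% | 58/489 = 11.86% | 46/465 = 9.89% |
| 24 | 70 | 70/465 = 15.05% | 70/489 = 14.31% | 46/465 = 9.89% |

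The ratio to the SRP version is 1.052 in every row. The gap from the SFAS version depends on what happened to the people outside it.

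**By arm**

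The same factor applies within each arm, using that arm's own counts. If the share outside the SFAS differs between arms, the two percentages are inflated by different factors. A participant who received the other arm's induction would also sit in one arm's numerator and the other arm's denominator.

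**Repeat summary**

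Suppose 50 randomised participants discontinue before Injection 1, all with a stopped attempt, and 10 of them are the only participants outside the SFAS (assumed counts). The possible denominators give:

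- all 50 of that group: 50/50 = 100%
- only the SFAS members of that group: 50/40 = 125%, which is not a valid percentage
- the whole SFAS: 50/479 = 10.4%

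The text does not choose among these.

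**The case against.** The strongest reply is that the gap is probably small and the importance modest. Induction randomisation takes place only once the TM buprenorphine dosing criteria are met (Protocol 4.1.2 and 9.4.1), and dosing follows after the pre-dose assessments, so few randomised participants may fall outside the SFAS. At 1% to 2% outside, the factor is only 1.010 to 1.021. Table 5 also calls receipt of the wrong arm highly unlikely, so the mixing of planned and actual arms may touch almost nobody. All of this stands, and it limits the size. It does not make the sentence consistent.

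A second reply is that an SFAS-only numerator may have been meant, in which case naming the SRP is the slip and the percentage would be right. The documents do not rule this out. SAP Table 1 records that version 3.0 updated the population for analysis in 5.7.2, which would fit one term having been changed and the other missed, but that is inference. Under either intention the paragraph needs correcting.

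A reader might also infer more than the text supports:

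- **That the reasons breakdown divides participants by attempts.** The paired use of respectively most naturally sets reasons against the number of attempts not continued. The unit is worth stating, but the text does not fix it wrongly.
- **That the repeat keeps the whole SFAS as its denominator.** The denominator is unstated.
- **That everyone outside the SFAS is especially likely to have a stopped attempt.** Nothing shows this for participants inducted by neither regimen: they were inducted, and SAP 5.7.6 repeats the primary retention analysis for them.
- **That this is a key tolerability measure.** The SAP places it under Other Analyses, and it is not among the endpoints in SAP Table 2.

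**Conclusion.** The mismatch is real, and no other section resolves it: the sentence names the SRP and divides by the SFAS. Taken as written, with the numerator counted in the SRP, the direction is certain, because the SFAS is a subset. The percentage equals the SRP proportion multiplied by N_SRP/N_SFAS.

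The size is not known. It is about 1% to 11% in relative terms if 1% to 10% of those randomised are outside the SFAS, and nil if the two sets coincide. Those shares are assumptions; the documents give no counts from which a large distortion could be claimed.

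The consequence is limited to a descriptive table. The primary retention analysis uses the Evaluable Population and its own rule, so the non-inferiority conclusion is unaffected.

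**What to change.** Amend the second paragraph of SAP 5.7.2 so that each percentage has one population:

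1. Participants with at least one non-continued attempt: SRP numerator over SRP denominator, both by planned arm. The SRP is the population the sentence already names, and it keeps everyone randomised in view.
2. Reasons: number of non-continued attempts with each reason over the total number of non-continued attempts, with the unit stated as attempts.
3. Repeat summary: denominator for the participant percentage is the randomised participants who discontinued before Injection 1, by planned arm.

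If the sponsor intended the SFAS instead, numerator and denominator should both say so, by actual arm, and the reference to the SRP should go.

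The cost is a few words in one paragraph and the matching table specification. No new data are needed and no other analysis changes.
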